4.2. Specification of Baseline Values

Participants will complete electronic headache diary entries daily for the 28-day run-in period, subjectively rating their headaches as mild, moderate, or severe and enter headache information (ie, occurrence of headache, duration of headache, maximum severity of headache, and acute headache medication use) about the previous day into the electronic headache diary device. If the participant is unable to complete the diary themselves then a parent/caregiver will complete the diary for them. Headache severity is collected in the diary on an 11-point numerical rating scale where mild is defined as a rating of 1-3, moderate as 4-6 and severe as 7-10. If the run-in period is greater or less than 28 days, the baseline values for calculating the change from baseline of the monthly values of the efficacy variables will be normalized to **28** days.

The efficacy baseline values during the 28-day run-in period derived from the e-diary include

- total number of migraine days
- total headache days of at least moderate severity
- total number of days of use of any acute headache medication
- total headache days of any severity
- total number of days of use of acute headache medications (triptans and ergot compounds, NSAIDs or paracetamol) for the group of participants who use acute headache medications at baseline
- total number of days with nausea or vomiting
- total number of days with photophobia and phonophobia

Other efficacy baseline values that will be measured on day 1 before the 1st IMP administration include

- disability score, as measured by the PedMIDAS assessment ([Appendix C](#))
- quality of life, as measured by the PedsQL questionnaire ([Appendix D](#))

Otherwise, baseline value will be the last non-missing value prior to the 1st dose of IMP, unless otherwise noted.

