The **monthly average number of days or hours** of efficacy variables (eg, migraine days, days of headache with at least moderate severity, days of headache with any severity, total hours of headache with any severity, total hours of headache with at least moderate severity, days of use of any acute headache medications, days with nausea or vomiting, days with photophobia and phonophobia etc.) **during the 12-week period** after the 1st dose of IMP will be derived and normalized to **28** days equivalent using the following formula.

$$\frac{\sum \text{Days or hours of efficacy variable over the 12 week period}}{\sum \text{Days with assessments recorded in the eDiary for the 12 week period}} \times 28 \quad (1)$$

The **monthly number of days or hours** of efficacy variables **during a 4-week period** after each dose will be derived and normalized to **28** days equivalent using the following formula, where monthly data separated by each visit of IMP dosing will be used.

$$\frac{\sum \text{Days or hours of efficacy variable during the 4 week period}}{\sum \text{Days with assessments recorded in the eDiary for the 4 week period}} \times 28 \quad (2)$$

The **baseline values** will be calculated using all data collected in the run-in period, ie,

$$\frac{\sum \text{Days or hours of efficacy variable during the run - in period}}{\sum \text{Days with assessments recorded in the eDiary for the run - in period}} \times 28 \quad (3)$$

The **percentage of reduction** in the monthly average number of an efficacy variable will be calculated as

$$\frac{\text{baseline value} - \text{postbaseline value}}{\text{baseline value}} \times 100\% \quad (4)$$

where the baseline value is calculated by formula (3) and the postbaseline value in the equation is calculated by formula (1) for the variables **during the 12-week period** or by formula (2) for the variables **during the 4-week period** after each dose for months 1, 2 and 3.

The FAS will be used for all efficacy analyses unless otherwise specified. Summaries will be presented by treatment group as randomized (test IMP or placebo IMP), unless otherwise noted. Descriptive statistics for all efficacy data will be presented by month or visit as appropriate and over 12-week period.

The primary and secondary endpoints analysis will be repeated for the per-protocol analysis set.

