6.4. Other Efficacy Endpoints

6.4.1. Definition

6.4.1.1. Electronic Headache Diary Data

For the purpose of this trial, a headache day of at least moderate severity will be defined as a calendar day (00:00 to 23:59) where the participant reports either of the following:

[figure not shown]
- headache pain that lasts ≥ 2 hours with a peak severity of at least moderate severity
- the participant used acute headache medication (NSAIDs, paracetamol, triptans or ergots) to treat a headache of any severity or duration

The derivation logic is presented in [Appendix B](#).

The percent reduction in the monthly average number of migraine days during the 12-week period after the 1st dose of IMP will be calculated by formula (4) in Section 6.1. The participant is considered as a responder reaching 50%, 75% or 100% reduction if his/her percent reduction is 50% or more, 75% or more, or 100% respectively. Similar definition will be applied to calculate the proportion of participants reaching at least 50%, 75% or 100% reduction in the monthly average number of headache days of at least moderate severity during the 12-week period after the 1st dose of IMP. If a participant is discontinued early from the trial, he/she will be counted as a non-responder.

The percent reduction in the monthly number of migraine days during the 4-week period after each dose for months 1, 2, and 3 will be calculated by formula (4) where the postbaseline value will be the number of headache days of at least moderate severity prorated to 28 days for month 1, month 2, and month 3, respectively. If the participant has 50% reduction or more in month 1, he/she will be considered responder during the 4-week period after 1st dose of IMP. In addition, if the participant also has 50% reduction or more in month 2 and 3, he/she is a responder for months 2 and 3, and the level of effect is sustained throughout the 12-week period after the 1st dose of IMP for this participant. Similar definition will be applied to calculate the proportion of sustained responders reaching at least 75% reduction. The proportion of sustained responders reaching at least 50% and 75% reduction in the number of headache days of at least moderate severity will be derived similarly.

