7. MULTIPLE COMPARISONS AND MULTIPLICITY

A fixed-sequence (hierarchical) testing procedure will be implemented to control the Type 1 error rate at 0.05. The sequence of comparisons will be as follows:

1. mean change from baseline (28-day baseline period) in the monthly average number of migraine days during the 12-week period after the first dose of IMP for the TEV-48125 treatment group versus the placebo treatment group
2. mean change from baseline (28-day baseline period) in monthly average number of headache days of at least moderate severity during the 12-week period after the first dose of IMP for the TEV-48125 treatment group versus the placebo treatment group
3. proportion of participants reaching at least 50% reduction in the monthly average number of migraine days during the 12-week period after the first dose of IMP for the TEV-48125 treatment group versus the placebo treatment group
4. mean change from baseline (28-day baseline period) in the monthly average number of days of use of any acute headache medications during the 12-week period after the first dose of IMP for the TEV-48125 treatment group versus the placebo treatment group
5. mean change from baseline (day 1) in migraine-related disability score, as measured by the Pediatric Migraine Disability Assessment (PedMIDAS) questionnaire, at 12 weeks after administration of the first dose of IMP for the TEV-48125 treatment group versus the placebo treatment group
6. mean change from baseline (day 1) in quality of life, as measured by the Pediatric Quality of Life Inventory (PedsQL), at 12 weeks after administration of the first dose of IMP for the TEV-48125 treatment group versus the placebo treatment group

If the resulting 2-sided p-value from the 1st comparison is ≤ 0.05 , then the next comparison of interest will be interpreted inferentially at the alpha level of 0.05. This process will continue either until all comparisons of interest are interpreted inferentially or until the point at which the resulting 2-sided p-value for a comparison of interest is > 0.05 . At the point where $p > 0.05$, no further comparisons will be interpreted inferentially.

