APPENDIX B. LOGICS FOR ENDPOINTS DERIVATION

Migraine day: 1 of the following 3 options				
		OPTION 1		
Part 1	1	A1 / A10	YES	
	2	A2 / A11	YES	
		AND		
		TWO OF THE FOLLOWING		
Part 2	1	A3 / A12	>=4	
	2	A4 / A13	YES	
	3	A5 / A14	YES	
	4	A6 / A15	YES	
		AND		
		ONE OF THE FOLLOWING		
Part 3	1	A7 / A16	YES	
	2	A8 / A17	YES	
		AND		
		A9 / A18	YES	
		OPTION 2		
		1	A1 / A10	YES
		2	B4 / B10	YES
		3	B5 / B11	ERGOT OR TRIPTAN OR NSAID OR PARACETAMOL
			OPTION 3	
		1	A1 / A10	YES
			AND	
			ONE OF THE FOLLOWING	
		1	B1 / B7	YES
		2	B2 / B8	YES

Headache day of at least moderate severity: 1 of the following 2 options			
OPTION 1			
1	A2 / A11	YES	
2	A3 / A12	Moderate (headache severity 4 to 6) or Severe (headache severity 7 to 10)	
OPTION 2			
1	B4 / B10	YES	
2	B5 / B11	ERGOT OR TRIPTAN OR NSAID OR PARACETAMOL	

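### SAP 6.4.1.1 defines monthly migraine-day reduction but fills the post-baseline term with headache days of at least moderate severity, so the month-level and sustained responders mix two variables if programmed literally

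*SAP*

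**What the plan says.** The third paragraph of SAP Section 6.4.1.1 sets out "The percent reduction in the monthly number of migraine days during the 4-week period after each dose for months 1, 2, and 3" and sends the reader to formula (4). The same sentence then specifies the post-baseline term: "where the postbaseline value will be the number of headache days of at least moderate severity prorated to 28 days". The rest of the paragraph builds responder rules on that value. A reduction of 50% or more in month 1 makes a month-1 responder. The same level in months 2 and 3 as well makes a sustained responder, and a 75% version follows. The paragraph closes by saying that the sustained 50% and 75% "reduction in the number of headache days of at least moderate severity will be derived similarly".

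Formula (4), in SAP Section 6.1, gives the percent reduction "in the monthly average number of an efficacy variable will be calculated as" baseline minus post-baseline, divided by baseline. Baseline comes from formula (3). The post-baseline value comes from formula (1) for the 12-week period "or by formula (2) for the variables" over each 4-week period.

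SAP Section 4.2 lists migraine days and "total headache days of at least moderate severity" as separate baseline variables. Appendix B derives them separately: three options for a migraine day, and for the other count, "Headache day of at least moderate severity: 1 of the following 2 options".

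**The concern.** The sentence names one variable and computes with another. It overrides only the post-baseline term, so the baseline term stays migraine days. The quantity is then neither a migraine-day reduction nor a headache-day reduction.

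Three results rest on it: the month-level 50% responder and the sustained 50% and 75% migraine-day responders. If programmed as written, they would not measure migraine-day response. They would also not be comparable with the 12-week responder, which uses migraine days throughout (SAP Sections 6.3.1.1 and 6.4.1.1).

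The SAP Introduction says the SAP prevails over the protocol where the two differ, so this text is the controlling specification. The note to file at the end of the SAP says the analysis has been run, and nothing visible tells a reader which variable produced these outputs.

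**Working it through.** **Plan's own figure.** Section 6.4.1.1 states no number to reproduce. The sample size in SAP Section 2.4 does not depend on this paragraph.

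**Step 1: are the two counts different?** Take Appendix B and two diary days on which no NSAID, paracetamol, triptan or ergot was taken.

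| Diary day (untreated) | Migraine day? | Headache day of at least moderate severity? |
|---|---|---|
| Mild pain (score 1 to 3), 2 hours or more, one-sided, throbbing, with nausea | Yes, Option 1: duration, two pain features, nausea | No: score below 4 |
| Moderate pain (score 4 to 6), 2 hours or more, no associated symptom, no aura | No: Options 1 and 3 fail | Yes, Option 1 |

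Neither count contains the other, so the gap between them can have either sign. A headache treated with one of the four listed drug classes meets Option 2 of both definitions and counts as both. That narrows the gap.

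**Step 2: size of the error.** Let B = baseline migraine days, M = migraine days in the month, and H = headache days of at least moderate severity in the month, all prorated to 28 days.

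- Intended: 100 × (B − M)/B
- As written: 100 × (B − H)/B
- Difference, as written minus intended: 100 × (M − H)/B

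Each day of gap therefore shifts the result by 100/B points: 12.5 at B = 8, 6.25 at B = 16, 3.57 at B = 28.

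**Step 3: when does status flip?** At the 50% cut, a false responder needs M > B/2 ≥ H, and a missed responder needs H > B/2 ≥ M. At the 75% cut, replace B/2 with B/4.

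**Step 4: illustrations at B = 16.** The counts are assumed, not trial data.

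| M | H | Intended | As written | Effect |
|---|---|---|---|---|
| 9 | 7 | (16 − 9)/16 = 43.75% | (16 − 7)/16 = 56.25% | False 50% responder |
| 7 | 9 | 56.25% | 43.75% | Missed 50% responder |
| 5 | 4 | (16 − 5)/16 = 68.75% | (16 − 4)/16 = 75% | False 75% responder |
| 16 | 12 | 0% | 25% | Reduction shown with no change |
| 16 | 20 | 0% | −25% | Increase shown with no change |

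**Step 5: does another reading rescue the sentence?** Suppose headache days were meant in both terms. The result would then not be a migraine-day reduction, and it would duplicate the headache-day version that the paragraph's last sentence lists separately. The text needs correction on that reading too.

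**Step 6: is it corrected elsewhere?** SAP Section 15 records two dropped subgroup analyses and one excluded site. The note to file deals only with the definition of a migraine day. Neither touches this sentence.

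**The case against.** The best answer is that context settles the intent. The sentence's subject is migraine days, formula (4) takes a single variable, and the headache-day version is listed separately at the end. A sensible programmer would use migraine days in both terms, and nothing in the documents shows that anyone did otherwise. This stands as far as it goes: the harm depends on the literal text having been programmed. It does not make the written rule right, and a validation programmer working from the specification could follow it exactly.

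The endpoints are exploratory and sit outside the fixed sequence in SAP Section 7 ("The sequence of comparisons will be as follows"). That is correct and limits the weight of the point.

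The exploratory analysis text in Section 6.4.2 is blacked out, so the variable may be restated there. That cannot be ruled out. The visible definition is still inconsistent.

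The day counts are invented and the documents give no joint distribution of the two counts, so the example gaps have no support from trial data. That is also fair: the arithmetic shows that misclassification is possible, not how common it is.

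Lastly, a change to the SAP text comes late. Section 2.5.2 has amendments approved before database lock, and the note to file, dated 29 May 2025, says the analysis was conducted. This affects the form of the remedy, not the need for one.

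**Conclusion.** The concern holds. The derivation rule in SAP Section 6.4.1.1 is wrong as written, and following it exactly gives a wrong value whenever the two monthly counts differ. The error is 100 × (M − H)/B points, in either direction, and zero when M = H. It changes responder status only when the cut (B/2 or B/4) falls between M and H. How many participants that would affect cannot be computed from the documents.

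The reach is limited to the month-level 50% and the sustained 50% and 75% migraine-day responders. The primary endpoint, the 12-week 50% responder, the fixed testing sequence and the sample size stand. Confidence in the wording defect is high. Any effect on reported results depends on how the program was written, which the documents do not show. The point should be corrected, but it does not threaten the trial's main conclusions.

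**What to change.** - Check which variable the responder program uses as the post-baseline value for months 1, 2 and 3.
- If it is headache days of at least moderate severity, re-run the month-level and sustained migraine-day responder outputs with migraine days.
- Record the correction in a note to file or the CSR: for these endpoints the post-baseline value in formula (4) is the number of migraine days from formula (2), and the headache-day version uses headache days of at least moderate severity at both baseline and post-baseline. If the SAP is reissued for any reason, correct the sentence there as well.

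A documented correction fits the sponsor's own practice. The existing note to file handles another internal SAP discrepancy in the same way, and protocol Section 9 requires changes after SAP finalization to be disclosed in the CSR.

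The cost is one program check and one short documented correction, plus a limited re-run only if the literal text was programmed. No new data are needed.

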6.4.2. Exploratory Efficacy Analysis**6.4.2.1. Electronic Headache Diary Data**

[REDACTED]

[REDACTED]

[REDACTED]

[REDACTED]

[REDACTED]

■ [REDACTED]

[REDACTED]

[REDACTED]

■ [REDACTED]

6.4.2.2. [REDACTED]

7. MULTIPLE COMPARISONS AND MULTIPLICITY

A fixed-sequence (hierarchical) testing procedure will be implemented to control the Type 1 error rate at 0.05. The sequence of comparisons will be as follows:

1. mean change from baseline (28-day baseline period) in the monthly average number of migraine days during the 12-week period after the first dose of IMP for the TEV-48125 treatment group versus the placebo treatment group
2. mean change from baseline (28-day baseline period) in monthly average number of headache days of at least moderate severity during the 12-week period after the first dose of IMP for the TEV-48125 treatment group versus the placebo treatment group
3. proportion of participants reaching at least 50% reduction in the monthly average number of migraine days during the 12-week period after the first dose of IMP for the TEV-48125 treatment group versus the placebo treatment group
4. mean change from baseline (28-day baseline period) in the monthly average number of days of use of any acute headache medications during the 12-week period after the first dose of IMP for the TEV-48125 treatment group versus the placebo treatment group
5. mean change from baseline (day 1) in migraine-related disability score, as measured by the Pediatric Migraine Disability Assessment (PedMIDAS) questionnaire, at 12 weeks after administration of the first dose of IMP for the TEV-48125 treatment group versus the placebo treatment group
6. mean change from baseline (day 1) in quality of life, as measured by the Pediatric Quality of Life Inventory (PedsQL), at 12 weeks after administration of the first dose of IMP for the TEV-48125 treatment group versus the placebo treatment group

If the resulting 2-sided p-value from the 1st comparison is ≤ 0.05 , then the next comparison of interest will be interpreted inferentially at the alpha level of 0.05. This process will continue either until all comparisons of interest are interpreted inferentially or until the point at which the resulting 2-sided p-value for a comparison of interest is > 0.05 . At the point where $p > 0.05$, no further comparisons will be interpreted inferentially.

8. SAFETY ANALYSIS

8.1. General

The safety population will be used for all safety analyses. Summaries will be presented by treatment group (TEV-48125 225 mg, TEV-48125 120 mg and placebo). TEV-48125 will be presented as actually received unless specified otherwise. A total column will also be provided.

For continuous variables, descriptive statistics (n, mean, SD, median, minimum, and maximum) will be provided for actual values and changes from baseline to each time point. For categorical variables, participant counts and percentages will be provided.

Missing values will be reported as missing and no imputation will be undertaken.

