**Table 2: Investigational Medicinal Products Used in the Trial**

IMP name	Test IMP	Placebo IMP
Trade name and INN, if applicable, or company-assigned number	Fremanezumab	None
Formulation	Sterile, clear to opalescent, colorless to slightly yellow solution for injection	Sterile, clear to opalescent, colorless to slightly yellow solution for injection
Unit dose strength(s)/dosage level(s)	225 mg monthly in participants with body weight $\geq 45.0$ kg at randomization (visit 2) 120 mg monthly dose in participants with body weight $< 45.0$ kg at randomization (visit 2)	Not applicable
Route of administration	Subcutaneous injection	Subcutaneous injection
Dosing instructions	Participants with body weight $\geq 45.0$ kg at randomization (visit 2): fremanezumab 225 mg: 1 active injection (225 mg/1.5 mL) at visits 2, 3, and 4  Participants with body weight $< 45.0$ kg at randomization (visit 2): fremanezumab 120 mg: 1 active injection (120 mg/0.8 mL) at visits 2, 3, and 4	Participants with body weight $\geq 45.0$ kg at randomization (visit 2): Placebo: single 1.5-mL injection at visits 2, 3, and 4  Participants with body weight $< 45.0$ kg at randomization (visit 2): Placebo: single 0.8-mL injection at visits 2, 3, and 4
Intervention type	Drug	Placebo
Packaging	IMP will be provided as follows: 
 
225 mg dose: PFS for single-use administration
 
120 mg dose: taken from two 2-mL vials each containing 0.5 mL of IMP for single-use administration
 
	Placebo will be provided as follows: 
 
1.5-mL injection: PFS for single-use administration
 
0.8-mL injection: taken from two 2-mL vials each containing 0.5 mL of placebo for single-use administration
 

IMP name	Test IMP	Placebo IMP
Manufacturer	      	      

IMP=investigational medicinal product; INN=international nonproprietary name; PFS=pre-filled syringe.

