#### **6.1.1.1.1. Starting Dose and Dose Levels**

Participants will be randomly assigned in a 1:1 ratio between test IMP and placebo IMP treatment groups:

- monthly sc administration of test IMP
- monthly sc administration of matching placebo IMP

The dose of test IMP to be administered will be determined by the participant's weight at randomization (visit 2):

- participants weighing  $\geq 45.0$  kg at randomization (visit 2) will receive monthly sc administration of test IMP at 225 mg.
- participants weighing  $<45.0$  kg at randomization (visit 2) will receive monthly sc administration of test IMP at 120 mg.

(Note: For this trial, monthly dosing refers to dosing approximately every 4 weeks [28 days].)

The recommended sc injection sites follow the National Institutes of Health (NIH) Clinical Center Patient Education Materials ([NIH Clinical Center Patient Education Materials 2016](#)). The suggested injection site locations for sc administration are the following: back of upper arms, lower abdomen/belly/waistline, and front of thighs. The sc injection and location will be recorded for each administration visit (visits 2, 3, and 4).

A 1.5 mL volume (participants weighing  $\geq 45.0$  kg at randomization [visit 2]) or a 0.8 mL volume (participants weighing  $<45.0$  kg at randomization [visit 2]) from each visit kit(s) (the full dose given with a PFS or taken from the vials) must be injected sc for administration to be considered complete. Participants randomized to the placebo IMP group will receive volume-matched doses of placebo IMP.

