6.2.4. Subgroup Analyses

The ANCOVA method will also be applied to the following subgroups for the change from baseline values in the number of migraine days and the monthly average number of headache days of at least moderate severity.

- participants receiving or not receiving any concomitant preventive treatment at baseline
- participants in different race groups (caucasian, non-caucasian)
- participants by age group (6-11 years, 12-17 years)
- participants by weight group
- participants by puberty status
- participants by sex
- participants by region

The model to be used in exploring the consistency of a treatment effect (ie, TEV-48125 – placebo) across the subgroup levels will have treatment, subgroup, and treatment-by-subgroup interaction as fixed effects, and a baseline covariate that corresponds to the respective endpoint (ie, response variable in the model). For ease of modeling purposes, a comparable cell means

parameterization will be used. Hence when assessing the treatment effect for change from baseline in number of migraine days in the age subgroup, the model will have treatment, age, and treatment-by-age interaction as fixed effects, and baseline number of migraine days as a covariate. Likewise, when assessing the treatment effect for change from baseline in number of migraine days in the weight subgroup, the model will have treatment, weight, and treatment-by weight interaction as fixed effects, and baseline number of migraine days as a covariate. For the by month analyses, MMRM will be performed in a similar manner in which the within subject covariance structure is the same as in Section 6.2.3.1. Actual rather than ‘as randomized’ stratification values will be used.

The estimated treatment effects at each subgroup level will be based on the least squares means treatment difference at each subgroup level and their corresponding two-sided 95% confidence intervals obtained from each of the respective models. Since there is a continuous covariate in each of these subgroup analyses, the least squares means will need to be adjusted to a common overall baseline value.

The results from the subgroup analysis will be displayed graphically using a forest plot.

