8.4. Adverse Events

All adverse events will be coded using the Medical Dictionary for Regulatory Activities (MedDRA).

For adverse event recording, the trial period is defined for each participant as the time period from signature of the informed consent form through completion of visit 5 or the early withdrawal visit for participants who withdraw from the trial for any reason.

Adverse events will be collected at each visit via adverse event inquiry.

The following are considered protocol-defined adverse events of special interest to be sent to the Sponsor's Pharmacovigilance Department for evaluation: ophthalmic related adverse events of at least moderate severity and severe hypersensitivity or anaphylactic reactions.

An adverse device effect is an adverse event related to the use of an investigational medical device or combination product. The full definition is provided in the trial protocol.

Events of possible drug-induced liver injury (AST or ALT $\geq 3 \times$ the ULN, total bilirubin $\geq 2 \times$ the ULN), or Hy's Law events, as well anaphylaxis and hypersensitivity reactions will be assessed. Hypersensitivity reactions will be monitored using the diagnostic criteria for anaphylaxis as

outlined by the 2006 Joint National Institute of Allergy and Infectious Disease/Food Allergy and Anaphylaxis Network Second Symposium on Anaphylaxis ([Sampson et al, 2006](#)). In the event of suspected anaphylaxis, vital signs, including oxygen saturation and respiration rate, will be measured.

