Summaries by treatment group will be presented for treatment emergent adverse events (overall and by severity), treatment emergent adverse device effects, treatment emergent adverse events determined by the investigator to be treatment-related adverse events (overall and by severity), adverse events determined by the investigator to be related to test IMP (and/or PFS) (ie, reasonable possibility) (defined as related or with missing relationship) (overall and by severity), serious adverse events, serious adverse device effects, protocol-defined adverse events of special interest, adverse events causing discontinuation from the trial, adverse device effects causing discontinuation from the trial, non-serious treatment emergent adverse events and prior to treatment adverse events. Additionally, the injection site reactions recorded as adverse events requiring concomitant or special treatment given and protocol defined adverse events of special interest will be summarized by treatment group separately.

The incidence of adverse event will be summarized using descriptive statistics by SOC, PT, and severity of the adverse event. Each participant will be counted only once within a SOC or a PT by using the adverse events with the highest severity within each category. Treatment-related adverse event summaries will include adverse events related to IMP and adverse events with missing relationship to IMP. Adverse events with the missing flag indicating serious will be excluded from the summary of serious adverse events but included in the summary of non-serious adverse events.

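### SAP 8.1 sets two weight-determined dose columns beside one pooled placebo column and names no all-fremanezumab column for safety

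*SAP*

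**What the plan says.** SAP 8.1 fixes the layout of the safety summaries: "Summaries will be presented by treatment group (TEV-48125 225 mg, TEV-48125 120 mg and placebo", with fremanezumab shown as actually received and a total column added. The SAP does not say what the total contains. Protocol 9.5 plans safety summaries by treatment group and for all participants, which points to everyone, placebo included.

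Efficacy is laid out differently. SAP 6.1 states "Summaries will be presented by treatment group as randomized (test IMP or placebo IMP), unless otherwise noted". For the weight subgroup, SAP 6.2.4 says "the model will have treatment, weight, and treatment-by weight interaction as fixed effects", so drug is compared with placebo inside each weight class.

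Randomisation is 1:1 between test IMP and placebo IMP, and weight at visit 2 then decides the dose (Protocol 4.1). Placebo follows the same rule: "Participants randomized to the placebo IMP group will receive volume-matched doses of placebo IMP" (Protocol 6.1.1.1.1). Presentation follows it too. Protocol Table 2 gives "225 mg dose: PFS for single-use administration" for the heavier class, whose 1.5 mL placebo also comes in a PFS. For the lighter class it gives the placebo as "0.8-mL injection: taken from two 2-mL vials each containing 0.5 mL of placebo for single-use administration".

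On device effects, SAP 8.4 says "An adverse device effect is an adverse event related to the use of an investigational medical device or combination product" and "Summaries by treatment group will be presented for treatment emergent adverse events (overall and by severity), treatment emergent adverse device effects". Adverse event (AE) tables are also split by age, 6-11 and 12-17 years.

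**The concern.** The two dose columns are not randomised groups. Each is a weight class within the test IMP arm, while the placebo column holds both classes. A difference between a dose column and placebo can therefore come from weight, injection volume or presentation as well as from the drug. The comparison that randomisation protects, all test IMP against all placebo, is used for efficacy but not named for safety.

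At stake is how safety by dose in children is read. These tables are the main display for that purpose, and the trial has no data monitoring committee (SAP 2.3) and no inferential safety analysis. No hypothesis test, estimate or stopping decision depends on them.

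**Working it through.** The plan gives no figure for table layout. The one numerical input taken from it is 139 randomised per arm (SAP 2.4), which reproduces: 133 / (1 - 0.04) = 138.5, rounded up to 139.

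**What is planned.** SAP 8.1 to 8.11 and SAP 9 name neither an all-fremanezumab column nor placebo by weight class. Weight splits appear only for efficacy subgroups (SAP 6.2.4) and drug concentrations (SAP 10). A total over all participants would not supply the missing contrast: with assumed rates of 20% on fremanezumab and 10% on placebo in equal arms, it shows 15%.

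**Notation.** Let w be the share below 45.0 kg, taken as equal in both arms. Weight is not a stratification factor (SAP 2.2), so chance imbalance is possible. The documents do not give w; I use 15, 25, 35 and 45%. All event rates below are also assumed.

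**Adverse device effects.** Suppose they arise only with the PFS, at rate p in both arms. The device parts in Protocol Table 5 are PFS and syringe components, the label and the instructions for use. Then:
- 225 mg column: p
- 120 mg column: 0
- placebo column: (1-w)p
- ratio of 225 mg to placebo: 1/(1-w)
- gap for 225 mg: wp

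All fremanezumab against all placebo has an expected ratio of 1.

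| w | Ratio 225 mg : placebo | Gap at p = 5% (points) |
|---|---|---|
| 15% | 1.18 | +0.75 |
| 25% | 1.33 | +1.25 |
| 35% | 1.54 | +1.75 |
| 45% | 1.82 | +2.25 |

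**Any other event, no drug effect.** With rate pL in the lighter class and pH in the heavier, pooled placebo shows w·pL + (1-w)·pH. The gap is -(1-w)(pH-pL) for 120 mg and +w(pH-pL) for 225 mg. Both are zero if the class rates are equal, and both change sign if the rates swap.

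**Would placebo of the same weight class be better?** Take pL = 45% and pH = 50%. Standard errors (SE) are binomial, conditional on class sizes, and RMS = sqrt(gap² + SE²). All entries are in points and refer to the 120 mg column.

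| w | Gap vs pooled | SE vs pooled | RMS vs pooled | SE vs matched (gap 0) |
|---|---|---|---|---|
| 15% | -4.25 | 11.7 | 12.4 | 15.4 |
| 25% | -3.75 | 9.4 | 10.2 | 11.9 |
| 35% | -3.25 | 8.3 | 8.9 | 10.1 |
| 45% | -2.75 | 7.6 | 8.1 | 8.9 |

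Here pooled placebo has the smaller total error at every w. With pH = 50%, matched placebo is closer only if pL is lower by more than 11.5, 9.6, 8.7 or 8.4 points respectively. The lighter placebo class would hold about 21 participants at w = 15% (0.15 × 139) and 63 at w = 45%. The SE for all fremanezumab against all placebo is 6.0 points throughout.

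**The case against.** The strongest reply is that little is lost. The two dose columns do not overlap, so all-fremanezumab counts can be added by hand. That stands, although medians cannot be pooled in this way.

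A reader might go further and infer that placebo by weight class is unrecoverable. The documents do not support that. SAP 8.4 lists adverse events and device effects by participant, SAP 9 lists local tolerability findings and SAP 8.6 lists laboratory results. SAP 5.7 lists physical examination results, which SAP 8.7 describes as including weight. Placebo events could probably be assigned to a weight class from these listings, though not from the summary tables.

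The age split covers all AE tables, which should include device effects and injection-site reactions, and potentially clinically significant limits are age-specific. This helps in part. Age is not the 45.0 kg cut, and laboratory, vital sign and ECG summaries have no such split.

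The total column is undefined, so an all-fremanezumab reading is not strictly excluded; Protocol 9.5 makes all participants the likelier one.

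Finally, weight-matched placebo is noisy and by the figures above often worse than pooled. That stands in full and limits that display to a supporting role.

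**Conclusion.** The point holds as a minor one: a cheap improvement to a descriptive display. The layout ties dose to weight class and presentation without doing the same for placebo, and leaves the randomised safety contrast for the reader to assemble. Device effects are the clearest case, because the direction follows from the design once such effects are assumed to arise only with the PFS. Even there the gap is 0.75 to 2.25 points at an assumed 5% rate.

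Two stronger readings should be resisted. A reader might infer that the SAP departs from the protocol. It need not: footnote j of Protocol Table 1 describes assignment to placebo or one of two weight-based doses, and showing safety by treatment received agrees with Protocol 9.1.1. A reader might also infer a large spurious drug effect. The documents give neither the share below 45 kg nor event rates by weight, so the size of any distortion is unknown and could be zero.

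**What to change.** - Add an all-fremanezumab column beside all placebo as the lead safety comparison, and keep the two dose columns.
- Define the total column as all participants.
- Present adverse device effects on a PFS-treated denominator: 225 mg PFS against placebo PFS.
- Optionally, for injection-site and local tolerability tables only, show placebo by weight class as a supporting descriptive display, with a note that the column below 45.0 kg is imprecise.

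No new data are needed: weight at randomisation already sets the dose, and weight group is already an efficacy subgroup. The cost is wider tables. The note to file at the end of the SAP indicates that the trial analysis has been conducted. If that includes the safety tables, these should be reported as supplementary outputs of the clinical study report and labelled post hoc; SAP 2.5.2 already provides an appendix for analyses that the SAP does not identify.
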